6.0 DOSE DELAYS/DOSE MODIFICATIONS

6.1 Dose Modification and Toxicity Management

Guidelines for the management of immune-mediated reactions, infusion-related reactions, and non-immune-mediated reactions for durvalumab are in the Dosing Modification and Toxicity Management Guidelines in Appendix B. Patients should be thoroughly evaluated and appropriate efforts should be made to rule out neoplastic, infectious, metabolic, toxin, or other etiologic causes of the imAE. Serologic, immunologic, and histologic (biopsy) data, as appropriate, should be used to support an imAE diagnosis. In the absence of a clear alternative etiology, events should be considered potentially immune related. In addition, there are certain circumstances in which durvalumab should be permanently discontinued (see section 5.4.1 and the Dosing Modification and Toxicity Management Guidelines in Appendix B).

Following the first dose of durvalumab, subsequent administration of durvalumab can be modified based on toxicities observed as described in the Dosing Modification and Toxicity Management Guidelines in APPENDIX B. Dose reductions are not permitted. Based on the mechanism of action of durvalumab leading to T-cell activation and proliferation, there is the possibility of observing immune related Adverse Events (irAEs) during the conduct of this study. Potential irAEs include immune mediated enterocolitis, dermatitis, hepatitis, and endocrinopathies. Subjects should be monitored for signs and symptoms of irAEs. In the absence of an alternate etiology (e.g., infection or PD) signs or symptoms of enterocolitis, dermatitis, hepatitis, and endocrinopathy should be considered to be immune-related.

Dose modification recommendations and toxicity management guidelines for immune-mediated reactions, for infusion-related reactions, and for non-immune-mediated reactions are detailed in Appendix B, Tables 1, 2, and 3 respectively.

In addition, management guidelines for adverse events of special interest (AESIs) are detailed in Appendix B, Table 1. All toxicities will be graded according to NCI CTCAE v4.03.

6.2 Study Restrictions and Concomitant Treatment

6.2.1 Contraception

Females of childbearing potential who are sexually active with a nonsterilised male partner must use 1 highly effective method of contraception from screening and must agree to continue using such precautions for 90 days after the final dose of investigational product; cessation of birth control after this point should be discussed with a responsible physician. Non-sterilized male partners of a female patient must use male condom plus spermicide throughout this period. Periodic abstinence, the rhythm method, and the withdrawal method are not acceptable methods of birth control. Female patients should also refrain from breastfeeding throughout this period.

- Females of childbearing potential are defined as those who are not surgically sterile (i.e., bilateral tubal ligation, bilateral oophorectomy, or complete hysterectomy) or postmenopausal.
- Women will be considered post-menopausal if they have been amenorrheic for 12 months without an alternative medical cause. The following age-specific requirements apply:
 - Women <50 years of age would be considered post-menopausal if they have been amenorrheic for 12 months or more following cessation of exogenous hormonal treatments and if they have luteinizing hormone and follicle-stimulating hormone levels in the post-menopausal range for the institution or underwent surgical sterilization (bilateral oophorectomy or hysterectomy).
 - Women ≥50 years of age would be considered post-menopausal if they have been amenorrheic for 12 months or more following cessation of all exogenous hormonal treatments, had radiation-induced menopause with last menses >1 year ago, had chemotherapy-induced menopause with last menses >1 year ago, or underwent surgical sterilization (bilateral oophorectomy, bilateral salpingectomy or hysterectomy).
- Highly effective methods of contraception, defined as one that results in a low failure rate (i.e., less than 1% per year) when used consistently and correctly are described in Table 2. Note that some

contraception methods are not considered highly effective (e.g., male or female condom with or without spermicide; female cap, diaphragm, or sponge with or without spermicide; non-copper containing intrauterine device; progestogen-only oral hormonal contraceptive pills where inhibition of ovulation is not the primary mode of action [excluding Cerazette/desogestrel which is considered highly effective]; and triphasic combined oral contraceptive pills).

- Nonsterilised males who are sexually active with a female partner of childbearing potential must use male condom plus spermicide (see Table 1) from Day 1 and for 90 days after receipt of the final dose of investigational product.

Table 1. Highly Effective Methods of Contraception (<1% Failure Rate)

| • Barrier/Intrauterine methods | • Hormonal Methods |
|--|--|
| 
 • Copper T intrauterine device • Levonorgestrel-releasing intrauterine system (e.g., Mirena®)^a | 
 • Implants: Etonogestrel-releasing implants: e.g. Implanon® or Norplant® • Intravaginal: Ethinylestradiol/etonogestrel-releasing intravaginal devices: e.g. NuvaRing® • Injection: Medroxyprogesterone injection: e.g. Depo-Provera® • Combined Pill: Normal and low dose combined oral contraceptive pill • Patch: Norelgestromin/ethinylestradiol-releasing transdermal system: e.g. Ortho Evra® • Minipill: Progesterone based oral contraceptive pill using desogestrel: Cerazette® is currently the only highly effective progesterone-based |

^a This is also considered a hormonal method

6.2.2 Blood donation

Subjects should not donate blood while participating in this study

6.2.3 Permitted Concomitant Medications

Investigators may prescribe concomitant medications or treatments (e.g., acetaminophen, diphenhydramine) deemed necessary to provide adequate prophylactic or supportive care except for those medications identified as “excluded” as listed in Section 6.2.4.

Table 2. Supportive Medications

| Supportive medication/class of drug: | Usage: |
|---|--|
| Concomitant medications or treatments (e.g., acetaminophen or diphenhydramine) deemed necessary to provide adequate prophylactic or supportive care, except for those medications identified as “prohibited,” as listed above | To be administered as prescribed by the Investigator |
| Best supportive care (including antibiotics, nutritional support, correction of metabolic disorders, optimal symptom control, and pain management [including palliative radiotherapy to non-target lesions, etc]) | Should be used, when necessary, for all patients |
| Inactivated viruses, such as those in the influenza vaccine | Permitted |

6.2.4 Excluded Concomitant Medications

The following medications are considered exclusionary during the study.

1. Any investigational anticancer therapy other than the protocol specified therapies
2. mAbs against CTLA-4, PD-1, or PD-L1 other than those under investigation in this study.
3. Any concurrent chemotherapy, radiotherapy, immunotherapy, biologic or hormonal therapy for cancer treatment, other than the protocol specified therapy. Concurrent use of hormones for noncancer-related conditions (e.g., insulin for diabetes and hormone replacement therapy) is acceptable.
4. Immunosuppressive medications including, but not limited to systemic corticosteroids at doses not exceeding 10 mg/day of prednisone or equivalent, methotrexate, azathioprine, and TNF- α blockers. Use of immunosuppressive medications for the management of investigational product-related AEs or in subjects with contrast allergies is acceptable. In addition, use of inhaled and intranasal corticosteroids is permitted. A temporary period of steroids will be allowed if clinically indicated and considered to be essential for the management of non-immunotherapy related events experienced by the patient (e.g., chronic obstructive pulmonary disease, radiation, nausea, etc).
5. Live attenuated vaccines within 30 days of durvalumab dosing (i.e., 30 days prior to the first dose, during treatment with durvalumab and for 30 days post discontinuation of durvalumab). Inactivated viruses, such as those in the influenza vaccine, are permitted.
6. EGFR TKIs should not be given concomitantly and should be used with caution in the 90 days post last dose of durvalumab. Increased incidences of pneumonitis (with third generation EGFR TKIs) and increased incidence of transaminase increases (with 1st generation EGFR TKIs) has been reported when durvalumab has been given concomitantly.
7. Herbal and natural remedies which may have immune-modulating effects.

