3.2 Exclusion Criteria

Subjects should not enter the study if any of the following exclusion criteria are fulfilled:

1. Participation in another clinical study with an investigational product during the last 3 weeks.
2. History of another primary malignancy except for:
 - Malignancy treated with curative intent and with no known active disease \geq 3 years before the first dose of study drug and of low potential risk for recurrence.
 - Adequately treated non-melanoma skin cancer or lentigo maligna without evidence of disease.
 - Adequately treated carcinoma in situ without evidence of disease eg, cervical cancer in situ, in-situ urinary bladder cancer, treated localized prostate cancer and ductal carcinoma-in situ.
 - Indolent hematological malignancies
3. Current or prior use of immunosuppressive medication within 14 days before the first dose of durvalumab, with the exceptions of intranasal, inhaled, topical steroids, or local steroid injections (e.g., intra articular injection), corticosteroids or systemic corticosteroids at physiological doses, which are not to exceed 10 mg/day of prednisone, or an equivalent corticosteroid, and steroids as premedication for hypersensitivity reactions (e.g., CT scan premedication).
4. Any unresolved toxicity (CTCAE grade 2) from therapy for a prior malignancy with the exception of alopecia, vitiligo, and the laboratory values defined in the inclusion criteria.
 - Patients with Grade \geq 2 neuropathy will be evaluated on a case-by-case basis after consultation with the Study Physician.
 - Subjects with irreversible toxicity that is not reasonably expected to be exacerbated by the investigational product may be included (e.g., hearing loss, peripherally neuropathy).
5. Any prior Grade \geq 3 immune-related adverse event (irAE) while receiving any previous immunotherapy agent, or any unresolved irAE >Grade 1.
6. Active or prior documented autoimmune or inflammatory disorders (including inflammatory bowel disease [e.g., colitis or Crohn's disease systemic lupus erythematosus, Sarcoidosis syndrome, or Wegener syndrome [granulomatosis with polyangiitis, Graves' disease, rheumatoid arthritis, hypophysitis, uveitis, etc]). No active diverticulitis within the previous 3 months. The following are exceptions to this criterion:
 - Patients with vitiligo or alopecia
 - Patients with hypothyroidism (e.g., following Hashimoto syndrome) stable on hormone

- replacement

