APPENDIX B
DOSING MODIFICATIONS AND TOXICITY MANAGEMENT GUIDELINES
Tables 1, 2 and 3

General Considerations Regarding Immune-Mediated Reactions

These guidelines are provided as a recommendation to support investigators in the management of potential immune-mediated adverse events (imAEs).

Immune-mediated events can occur in nearly any organ or tissue, therefore, these guidelines may not include all the possible immune-mediated reactions. Investigators are advised to take into consideration the appropriate practice guidelines and other society guidelines (e.g., National Comprehensive Cancer Network (NCCN), European Society of Medical Oncology (ESMO)) in the management of these events. Refer to the section of the table titled “Other -Immune-Mediated Reactions” for general guidance on imAEs not noted in the “Specific Immune-Mediated Reactions” section.

Early identification and management of imAEs is essential to ensure safe use of the study drug. Monitor patients closely for symptoms and signs that may be clinical manifestations of underlying imAEs. Patients with suspected imAEs should be thoroughly evaluated to rule out any alternative etiologies (e.g., disease progression, concomitant medications, infections). In the absence of a clear alternative etiology, all such events should be managed as if they were immune-mediated. Institute medical management promptly, including specialty consultation as appropriate. In general, withhold study drug/study regimen for severe (Grade 3) imAEs. Permanently discontinue study drug/study regimen for life-threatening (Grade 4) imAEs, recurrent severe (Grade 3) imAEs that require systemic immunosuppressive treatment, or an inability to reduce corticosteroid dose to 10 mg or less of prednisone or equivalent per day within 12 weeks of initiating corticosteroids.

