| | Grade 2 | 
Hold study drug/study regimen dose until Grade 2 resolution to \leq Grade 1
 
 • • If toxicity improves to \leq Grade 1 then the decision to reinstate study drug/regimen will be based upon treating physician's clinical judgment and after completion of steroid taper (\leq 10mg prednisone or equivalent). | 
For Grade 2
 
 - Monitor symptoms daily and consider hospitalization - Obtain Pulmonary and Infectious Diseases Consults; consider discussing with Clinical Study Lead, as needed. - Promptly start systemic steroids (e.g., prednisone 1-2mg/kg/day PO or IV equivalent) - Reimage as clinically indicated, consider chest CT with contrast and repeat in 3-4 weeks. - If no improvement within 2 to 3 days, additional workup should be considered and prompt treatment with IV methylprednisolone 2-4mg/kg/day started - If no improvement within 2-3 days despite IV methylprednisolone at 2-4/g/kg/day, promptly start immunosuppressive therapy such as tumor necrosis factor (TNF) inhibitors (e.g. infliximab at 5mg/kg IV once, may be repeated at 2 and 6 weeks after initial dose at the discretion of the treating provider or relevant practice guidelines). Caution: Important to rule out sepsis and refer to infliximab label for general guidance before using infliximab. Consider, as necessary, discussing with Clinical Study Lead. |

| | | | |
|--|---------------------|--|---|
| | Grade 3 or 4 | Permanently discontinue study drug/study regimen | 
For Grade 3 or 4
 
 - Promptly initiate empiric IV methylprednisolone 1 to 4 mg/kg/day or equivalent - Obtain Pulmonary and Infectious Diseases Consults; consider; discussing with Clinical Study Lead as needed. - Hospitalize the patient - Supportive Care (e.g., oxygen,) - If no improvement within 2 days, additional workup should be considered and prompt treatment with additional immunosuppressive therapy such as TNF inhibitors (e.g. infliximab at 5mg/kg IV, may be repeated at 2 and 6 weeks after initial dose at the discretion of the treating provider or relevant practice guidelines). Caution: rule out sepsis and refer to infliximab label for general guidance before using infliximab |
|--|---------------------|--|---|

| | | | |
|------------------------------|---|-------------------------|---|

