| | Grade 2 | 
Hold study drug/study regimen until resolution to \leq Grade 1
 
 • • If toxicity improves to $<$ Grade 1 then study drug/study regimen can be resumed after completion of steroid taper (<10 mg prednisone, or equivalent). | 
For Grade 2:
 
 - Consider symptomatic treatment including hydration, electrolyte replacement, dietary changes (e.g., American Dietetic Association colitis diet), and loperamide and/or budesonide - Promptly start prednisone 1 to 2 mg/kg/day PO or IV equivalent - If event is not responsive within 2 to 3 days or worsens despite prednisone at 1-2 mg/kg/day PO or IV equivalent, consult a gastrointestinal (GI) specialist for consideration of further workup such as imaging and/or colonoscopy to confirm colitis and rule out perforation, - If still no improvement within 2 to 3 days despite 1 to 2 mg/kg IV methylprednisolone, promptly start immunosuppressant agents such as infliximab at 5mg/kg IV, may be repeated at 2 and 6 weeks after initial dose at the discretion of the treating provider or relevant practice guidelines. Caution: Important to rule out bowel perforation and refer to infliximab label for general guidance before using infliximab - If perforation is suspected, consult a surgeon experienced in abdominal surgery immediately without any delay. - Consider, as necessary, discussing with Clinical Study Lead if no resolution to \leq Grade 1 in 3 to 4 days. |

| | | | |
|---|---|---|--|

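### Section 6.2.4 item 4 bans systemic steroids at up to 10 mg/day on study, the same doses that exclusion criterion 3 accepts at entry: the threshold is inverted

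*Combined protocol and SAP*

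**What the plan says.** Section 6.2.4 of the protocol opens with "The following medications are considered exclusionary during the study". Item 4 of that list then reads "Immunosuppressive medications including, but not limited to systemic corticosteroids at doses not exceeding 10 mg/day of prednisone or equivalent, methotrexate, azathioprine", followed by TNF-α blockers.

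Item 4 carries its own exceptions: treatment of drug-related adverse events, contrast allergy, inhaled and intranasal steroids, and short courses for other events ("A temporary period of steroids will be allowed if clinically indicated"). Item 3 of the same list adds "Concurrent use of hormones for noncancer-related conditions (e.g., insulin for diabetes and hormone replacement therapy) is acceptable".

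At entry, exclusion criterion 3 in Section 3.2 bars immunosuppressive medication in the 14 days before the first dose of durvalumab. Its exceptions include "systemic corticosteroids at physiological doses, which are not to exceed 10 mg/day of prednisone, or an equivalent corticosteroid".

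Appendix B deals with steroids given for immune-mediated events. Its general considerations require permanent discontinuation for, among other things, "inability to reduce corticosteroid dose to 10 mg or less of prednisone or equivalent per day within 12 weeks of initiating corticosteroids". For Grade 2 colitis it says that "study drug/study regimen can be resumed after completion of steroid taper (<10 mg prednisone, or equivalent".

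**The concern.** An upper dose limit belongs in an exception, not in a prohibition. Criterion 3 uses it as an exception: systemic steroids are barred unless the dose is at or below 10 mg/day. Item 4 places the same limit inside the list of banned drugs, so the low doses become the ones named as banned. It looks as though the exception was carried over without the words that made it one.

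What is at stake is conduct, not analysis. Section 6.2.3 allows any supportive medication except those listed in 6.2.4, so 6.2.4 is the list that sites work from. A patient who enters under criterion 3 on a stable low dose would, on the literal text, be in breach from the first infusion. Sites could then differ in whether they stop the steroid, record a deviation, or ignore the wording.

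**Working it through.** No arithmetic applies beyond a count, so the check sets the rules side by side.

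**The two rules on background steroid use**

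| Place | Function of the rule | Status of systemic steroids at ≤10 mg/day |
|---|---|---|
| Section 3.2, criterion 3 | Entry, 14 days before first dose | Accepted, at physiological doses |
| Section 6.2.4, item 4 | During the study | Named as prohibited |

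The dose and the drug class are the same. Only the direction differs.

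**Do the exceptions close the gap?** Taking those in 6.2.4 in turn:

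- Drug-related adverse events and contrast allergy: a steady dose brought in from before the study is neither.
- Inhaled and intranasal use: not systemic.
- Temporary courses for other events: an ongoing stable dose is not temporary.
- Hormone replacement (item 3): this arguably covers adrenal replacement. The endocrinopathy rows of Appendix B also allow retreatment in patients who need continued steroid replacement.

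What is left uncovered is stable, low-dose systemic use that is not hormone replacement.

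**Are higher doses let through?** No. Item 4 is worded as an open-ended list of immunosuppressive medications, so doses above 10 mg/day remain prohibited under the general term. The error is that low doses are named, not that high doses are released.

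**Which direction was meant?** The documents state a 10 mg prednisone level 13 times:

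- criterion 3: 1
- Section 6.2.4 item 4: 1
- Appendix B, general considerations: 1
- Appendix B, restart rules: 10, made up of pneumonitis Grade 2 (1), colitis Grade 2 and Grade 3 (2), hepatitis Grade 2 and Grade 3 or 4 (2), pancreatitis (1), nephritis Grade 2 (1), rash Grade 2 and Grade 3 (2) and endocrinopathy (1)

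Total: 1 + 1 + 1 + 10 = 13. Of the 10 restart rules, 1 uses ≤10 mg (pneumonitis), 8 use <10 mg, and 1 prints the dose with no sign (rash Grade 3), as the end of the taper. In 12 of the 13 statements, 10 mg marks the ceiling, inclusive or not, of what is tolerable. Item 4 alone lists doses up to that level as excluded.

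**The case against.** The wording conflict cannot be explained away, but there is a fair case that it matters little.

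- **The affected group is very small.** Criterion 6 bars most active or prior autoimmune and inflammatory disorders, and criterion 18 bars interstitial lung disease and pneumonitis. As a clinical judgement not stated in the documents, these are common reasons for long-term low-dose prednisone. This stands, and it is the main reason the number affected may be zero.
- **Criterion 3 speaks of physiological doses.** If that means replacement use only, item 3 of 6.2.4 already permits it and the two rules hardly collide. If it describes a dose level, they do. The second reading is at least as natural, so this narrows the point without removing it.
- **The count of 13 is weak evidence.** The 10 restart rules are near-copies of one template, and with the general discontinuation rule they concern treatment of immune-mediated events, which item 4 expressly allows. This stands: Appendix B shows the intended direction but does not contradict item 4. The direct contradiction is one rule against one, criterion 3 against item 4.
- **Little follows from a breach.** Section 5.4.1 does not list a prohibited steroid as a reason to stop durvalumab, and the IRB form's category for failure to follow the protocol also requires greater risk of harm to subjects. The practical effect is probably confined to how deviations are classified.

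It could also be argued that on-study rules may be stricter than entry rules. A stricter rule would ban systemic steroids without a dose, as item 4 does for methotrexate and azathioprine. A ban that names only the lower doses makes no sense as a tightening.

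**Conclusion.** The concern holds. Item 4 of Section 6.2.4 names as prohibited the dose range that criterion 3 accepts, none of the exceptions covers stable low-dose use outside hormone replacement, and no other section corrects it.

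The size is minor. Few patients, possibly none, would be affected; no count can be given because the documents report no rate of low-dose systemic steroid use. A site that reads the whole protocol would probably recognise the slip. The major pathological response comparison, the secondary analyses, the sample size and the power are untouched.

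The conclusion rests on reading *physiological doses* in criterion 3 as a dose level and on treating adrenal replacement as allowed under item 3.

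**What to change.** In Section 6.2.4 item 4, delete *not*, so that the phrase covers systemic corticosteroids at doses exceeding 10 mg/day of prednisone or equivalent. Alternatively, keep systemic corticosteroids in the list without a dose and add doses up to 10 mg/day to the exceptions that follow. Criterion 3, item 3 and Appendix B need no change.

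The cost is one word, or one short phrase, at the next protocol amendment. No data collection or analysis is affected.
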